10.9.3. Vital Signs

Vital signs parameters to be summarised are:

- Heart Rate (beats per minute), systolic blood pressure (mmHg), diastolic blood pressure (mmHg), respiratory rate (breaths per minute), peripheral arterial oxygen saturation (%) and tympanic temperature (°C).

Vital signs parameters will be summarised as observed parameter values and changes from baseline, by treatment group for all scheduled protocol visits, where baseline is defined as the assessment performed prior to the first administration of IMP.

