10.7. Appendix 7: Definitions

10.7.1. General

TERM	hVIVO Services Limited Definition
Completion (of a participant's participation in the study)	A participant will be considered to have completed the study after his/her attendance at the last planned study visit, or the last unscheduled visit as applicable.
Baseline	For safety assessments the nearest assessments completed prior to inoculation will be used as the baseline measure, unless stated otherwise.
Enrolment (of a participant into the study)	A participant will be considered to be 'enrolled' into the study once he/she has been inoculated. Potential participants who are screened for the purpose of determining suitability for the study, but do not participate in the study, are not considered enrolled, unless otherwise specified by the protocol.
First study visit (of a participant)	The visit in which the study-specific consent is signed.
Infectious titre	The titre of inoculum producing viral infection in a participant. The term 'titre' applies to the quantity or concentration of inoculum (depending on the units documented).
Quarantine group	A group of participants who are admitted to and are resident in the quarantine unit for a particular quarantine period (i.e., participants whose Day 0 and scheduled discharge date are the same).
Quarantine period	The period when clinical study participants are isolated in the quarantine unit during an HVC study.
Randomisation number	The number allocated to a participant at randomisation, generated as stated in the protocol (NB. Not applicable will be recorded for "screen fail" participants or participants who are not randomised).
Subject number	The unique number assigned to a subject in the hVIVO subject database, which is used to identify the subject prior to randomisation. This number will be used throughout the recruitment and generic screening process to identify the subject.
Challenge	The inoculation of a participant with challenge agent inoculum. By definition, the day of challenge is Day 0.

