6. STUDY DESIGN

6.1. Summary of Study Design

This is a single-centre, randomised, double-blind, placebo-controlled, proof-of-concept study in healthy adult male and female participants from 18 to 55 years of age, inclusive. The primary goal of this Phase 1b study is to assess the antiviral activity of RV299 against RSV in the viral challenge model. In addition, the safety, tolerability, and PK of RV299 will be assessed.

A total of 80 participants is planned to be enrolled in this study: 40 participants on RV299 and 40 participants on placebo.

The study is divided into the following study phases:

- Screening phase: from Day -90 to Day-3 pre-human viral challenge (HVC). Historical generic screening data collected through the hVIVO generic screening process may be transferred to this study after the study-specific consent form has been signed by the participant.
- Inpatient phase: Participants will be resident in the quarantine unit for approximately 15 days (from Day -2 to Day 12). Procedures will include:
 - Pre-HVC:
 - Admission to quarantine unit on Day -2/-1.
 - Baseline assessments will be conducted as per Schedule of Events (SoE) up to Day 0, pre-challenge.
 - HVC: RSV-A Memphis 37b virus inoculation on Day 0.
 - Post-HVC:
 - Randomisation to receive RV299 or matched placebo.
 - Administration of IMP (RV299/placebo). Each participant will receive IMP twice daily (~12 hours interval) for 5 consecutive days:
 - IMP dosing to start on confirmation of RSV infection, i.e., after a positive result by qualitative integrative cycler polymerase chain reaction (qicPCR). The qicPCR of nasal wash will be performed twice daily on Days 2-5 (Day 5 morning only), or until a positive result is received, whichever is sooner. The earliest start of IMP dosing will be in the evening of Day 2 post-HVC (IMP will be initiated 12 hours \pm 1-hour post nasal wash confirmation of infection)
 - OR
 - IMP would start in the evening of Day 5, if no positive result obtained by qicPCR
 - Day 1 onwards and each day study assessments will be conducted as per SoE.
 - Participants will be discharged from the quarantine unit on Day 12 (or may remain longer at the discretion of the principal investigator [PI]/investigator).
- Outpatient phase:
 - Final visit: Day 28 (\pm 3 days).

The overall study design is depicted in

Table 1.

Table 1: Study Schematic: On-study Participant Progression

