10. PLANNED STATISTICAL METHODS

10.1. Statistical Considerations

10.1.1. General Definitions

In all applicable summary/analysis presentations of safety endpoints, Baseline is defined as the last non-missing assessment value for a participant, for that particular parameter, that is prior to inoculation of challenge virus, unless over-ruled after review of data at the BDRM or otherwise stated in the appropriate endpoint sections below, whatever the reason for that assessment (e.g. if it is a repeat assessment, then it should be used as the baseline). For efficacy endpoints, the baseline definition is as per the appropriate endpoint sections below. For the derivation of most efficacy endpoints, the first assessment to be used should be the assessment that was taken at the time of first administration of IMP. For example, if a participant was first dosed on the morning of Day 3 then the first qRT-PCR value to be used in the AUC of qRT-PCR viral load (from time of first administration) derivation should be the Day 3 morning assessment. For endpoints using symptom diary card data, the definition of baseline will be defined in greater detail within the appropriate sections of the SAP.

A participant will be classed as infected, and therefore randomised to be dosed, when they have a positive result for RSV-A Memphis 37b by qualitative integrative cycler polymerase chain reaction (qicPCR) from nasal wash sample. IMP administration will be initiated 12 hours after a positive result. However, if a participant remains uninfected, IMP administration will begin on the evening of Day 5.

For participants that extend their time in quarantine beyond Day 12, the additional assessments beyond Day 12 will be listed only, and will not be used for the derivation of any efficacy endpoints. For the avoidance of doubt, the assessment performed on the morning of Day 12 will be the final assessment used for all analyses and summaries for all participants. If additional assessments are taken on Day 12, then they will be listed only. However, the use of data beyond the morning of Day 12 will be discussed at the BDRM.

A participant will be considered to have completed the study after their attendance at the last planned study visit (Day 28 (\pm 3 days)), or the last unscheduled visit (if any occur), as applicable.

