10.7.1.2 Sensitivity Analyses

1. The first sensitivity analysis of the AUC of RSV viral load measured in nasal washes by qRT-PCR will be presented for a fixed time period, from the last measurement collected prior to the first administration of IMP to the scheduled assessment occurring 6.5 days afterwards (e.g. if a participant does not have a positive qPCR then they will be dosed on Day 5 (evening) and they will be followed up to the morning of Day 12 with 14 assessments in total) – which represents the AUC over the longest possible time period over which all subjects are sampled.
2. A second sensitivity analysis of the AUC of RSV viral load measured in nasal washes by qRT-PCR will be presented for a fixed time period, which will include data from the morning assessment on Day 2 (i.e. the first qRT-PCR assessment measured) through to the morning of Day 12.
3. A third sensitivity analysis of the AUC of RSV viral load measured in nasal washes by qRT-PCR, from the last measurement collected prior to the first administration of IMP until the last measurement collected up to the morning of Day 12 (Quarantine discharge), will be presented where the AUC will be calculated using unlogged viral load data (i.e. the supplied value will be anti-logged to get a value as copies/mL).

The AUC analyses will be summarised by treatment group. The same statistical testing methods as applied to the main analysis of the primary endpoint will be applied to each sensitivity analysis. For the third sensitivity analysis, the data will be log-transformed (base 10) prior to statistical analysis.

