[Line graph: y-axis = mean of total symptoms score, x-axis = day relative to dosing (the axis will be negative to include days prior to IMP administration), one line for each treatment group on same plot].

A boxplot will also be presented by day (relative to first dose of IMP) and assessment, plotting the median and mean qRT-PCT values for each treatment group, with the corresponding summary statistics.

[Box plot: y-axis = mean of qRT-PCR (\log_{10} copies/mL), x-axis = day relative to dosing, one box-and-whisker for each day, with each treatment panelled with RV299 at the top and placebo below].

Note: For multiple assessments taken within each day, so as to be able to plot mean values across participants (within a treatment group) by day, the actual collection time point (which may differ across participants) will not be used. Rather all first, second and third assessments will have mean values separately calculated and plotted as three means within each day. These three means will be shown equally spaced along the x-axis within the graph.

Area under the Curve over Time of Total Clinical Symptoms Change from Baseline (TSS-AUC-CFB) as Measured from 10 Symptoms within the Graded Symptom Scoring System Collected 3 Times Daily Starting at Initial Administration of IMP up to Planned Discharge from Quarantine

The change from baseline will be calculated for each assessment following administration of IMP and an AUC calculated using these scores will be analysed in the same manner as described above

(including sensitivity analyses 1 and 2), where the baseline assessment is the assessment nearest to the time of the first administration of IMP (can be prior to or after dosing, depending on whether dosed in the morning or evening).

Peak Symptoms Diary Card Score: Peak Total Clinical Symptoms (TSS) as Measured from 10 Symptoms within the Graded Symptom Scoring System Collected 3 Times Daily Starting from Initial Administration of IMP up to Planned Discharge from Quarantine

Using the scheduled protocol assessments from the assessment at the time of the first dose of IMP to Day 12 (Quarantine discharge), the highest total symptom score (defined as the sum of all 10 individual composite symptoms) will be summarised by treatment group and modelled in the same way as the main analysis of the primary endpoint.

Participants who do not record any symptoms will be assigned a peak of 0.

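### Two change-from-baseline outputs start before their own baseline: the Day 2 to Day 12 symptom-change AUC (Table 14.2.3.2.3) and vital-sign change by study day (Table 14.3.7)

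*SAP*

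**What the plan says.** **Timing of first dose.** SAP 6.1: "The earliest start of IMP dosing will be in the evening of Day 2 post-HVC". Participants with no positive qicPCR start on Day 5 evening.

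**Symptoms.** For TSS-AUC-CFB, SAP 10.7.2.4 states: "The change from baseline will be calculated for each assessment following administration of IMP". The baseline is the diary card closest in time to first IMP, before or after it. The same sentence extends sensitivity analyses 1 and 2 to this endpoint. SAP 10.7.1.2 describes the second as a fixed period "which will include data from the morning assessment on Day 2", ending on Day 12 morning. Table 14.2.3.2.3 is planned for it.

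**Vital signs.** SAP 10.9.3 requests, beside the observed results, "changes from baseline, by treatment group for all scheduled protocol visits". The reference for those changes is set later in the same sentence and is tied to first dosing: "baseline is defined as the assessment performed prior to the first administration of IMP". The Schedule of Events has vital signs once daily after Day 0. SAP 10.1.2 reserves days counted from IMP for clinical-symptom efficacy and PK outputs, so vital signs stay on study day. Table 14.3.7 borrows the Table 14.3.2 shell, which repeats only post-baseline assessments.

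**General baseline rules.** Protocol 10.7.1: "For safety assessments the nearest assessments completed prior to inoculation will be used as the baseline measure, unless stated otherwise". SAP 10.1.1 sets the safety baseline "prior to inoculation of challenge virus, unless over-ruled after review of data at the BDRM or otherwise stated in the appropriate endpoint sections below". The introduction to Protocol section 8 instead takes the pre-dose value closest to dosing, unless stated otherwise. Note c to the Schedule of Events names Day -1 as the symptom diary baseline.

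**The concern.** A baseline that moves with each participant's first dose is paired with output windows fixed to study day. Where the window opens first, the change score has no reference value yet.

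For symptoms, a programmer must choose between leaving the pre-dose part out, so that Table 14.2.3.2.3 no longer covers Day 2 to Day 12, and subtracting a later score from an earlier one. Under the second choice, a participant who is well on Days 2-4 and ill at dosing collects negative area for hours of being well. The table carries a treatment comparison modelled like the primary endpoint, so it needs one fixed derivation before unblinding.

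For vital signs, an early study-day row would show a fall simply because the later reference value was higher. No table of vital-sign change from a pre-inoculation value is planned.

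**Working it through.** Time is counted in days, with morning = .0 and evening = .5.

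**The SAP's own figure.** SAP 10.7.1.2 gives 6.5 days and 14 assessments for a Day 5 evening start. 12.0 - 5.5 = 6.5 days; twice-daily points from Day 5 evening to Day 12 morning inclusive number 14. Both are reproduced.

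**Possible starts.** qicPCR runs from Day 2 morning to Day 5 morning and dosing follows about 12 h after a positive sample. That gives seven start slots, s = 2.5 to 5.5.

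**Symptom window.** Length = 24 × (12 - 2) = 240 h. Pre-IMP part = 24 × (s - 2) h; share = (s - 2)/10.

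**Vital signs.** Assumptions: one reading each morning, before any dose in the same slot, with the last pre-IMP reading as baseline. SAP 10.9.3 does not itself say last, and no clock time is given.

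| First IMP | Pre-IMP part of the 240 h | Share | Vital-sign baseline | Study days before it |
|---|---|---|---|---|
| Day 2 evening | 12 h | 5% | Day 2 | Day 1 |
| Day 3 morning | 24 h | 10% | Day 3 | Days 1-2 |
| Day 3 evening | 36 h | 15% | Day 3 | Days 1-2 |
| Day 4 morning | 48 h | 20% | Day 4 | Days 1-3 |
| Day 4 evening | 60 h | 25% | Day 4 | Days 1-3 |
| Day 5 morning | 72 h | 30% | Day 5 | Days 1-4 |
| Day 5 evening | 84 h | 35% | Day 5 | Days 1-4 |

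At other clock times the vital-sign baseline is the same day or one day earlier. In no case does Day 5 precede it.

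**Size of the symptom effect if pre-dose scores are used (assumed scores).** Take a Day 5 evening start, a score of 0 on every earlier card and a score of 4 at baseline, with the baseline card at the time of dosing. Each earlier change score is 0 - 4 = -4.
- As a rectangle: -4 × 84 = -336 score-hours.
- By the trapezoidal rule, with cards about 8 h apart and the change returning to 0 over the last gap: -4 × (84 - 8) + ½ × (-4) × 8 = -304 - 16 = -320 score-hours.

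**Vital-sign illustration (assumed values).** Temperature is 36.6 °C before inoculation and on Day 1, 37.6 °C on Day 5 before dosing, and 38.0 °C on Day 6. The pre-IMP baseline gives 36.6 - 37.6 = -1.0 on Day 1 and 38.0 - 37.6 = +0.4 on Day 6. The pre-inoculation baseline gives 0.0 and 38.0 - 36.6 = +1.4.

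**Does the shell settle it?** With morning readings, Days 3 and 4 are post-baseline for early starters, but are the baseline itself or earlier for others. Day 2 joins them if readings follow the evening dose. Restricting rows to post-baseline assessments therefore leaves open whether these rows drop the later starters or keep their pre-baseline changes.

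**The case against.** **Protocol departure.** A reader might infer from Protocol 10.7.1 that the pre-IMP baseline breaches the protocol and should have been listed in SAP section 11. The documents do not support this. Protocol 10.7.1 and SAP 10.1.1 both allow exceptions, and Protocol section 8 itself favours the value closest to dosing. Laboratory and ECG baselines in the SAP are also pre-IMP, which suggests a deliberate choice. What remains is that two protocol sentences give different defaults and need reconciling.

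**Hidden virus effect.** It is tempting to say that a mid-infection baseline conceals fever caused by the challenge. Observed values are tabulated beside the changes, and Listing 16.2.10 flags every temperature of 37.9 °C or more. The endpoints named for challenge-virus safety are related AEs, related SAEs and concomitant medication. Safety output is descriptive, so no test is touched. This objection stands: the harm is to the reading of the change columns.

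**Pre-baseline changes are not certain to be tabulated.** The shell points away from them for vital signs, and the post-IMP restriction points away from them for symptoms. That is fair. The negative area is therefore conditional, and the defect is conflicting instructions rather than a clearly specified wrong calculation.

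**Treatment bias.** The same rule applies in both arms, and nothing here shows a bias in favour of either.

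**Conclusion.** The point holds as an internal contradiction in two planned outputs. Table 14.2.3.2.3 cannot be produced from the SAP as written without an unstated choice affecting 5% to 35% of each participant's window. The figure of about -320 to -336 score-hours is the latest-start case and applies only if pre-dose scores are used; it rests on the assumed score of 4 and the assumed symptom-free period. It scales with the baseline score: a score of 2 would give -2 × 84 = -168 by the rectangle.

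For vital signs, the text and shell of Table 14.3.7 disagree, and one to four study days per participant are affected under the morning-reading assumption.

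The reach is limited: one sensitivity analysis of a secondary endpoint, and the change columns of one descriptive safety table. The primary endpoint, its sensitivity analyses and the main TSS-AUC-CFB analysis are unaffected. The change is still worth making, because it is cheap and avoids a programming choice that the SAP has not settled.

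**What to change.** - **SAP 10.7.2.4 and Table 14.2.3.2.3:** drop sensitivity analysis 2 for TSS-AUC-CFB and keep it for TSS-AUC, where nothing is subtracted. Alternatively, keep the table with the Day -1 diary baseline from note c. No part of the window would then precede baseline (0 h instead of 12-84 h). The SAP would need to allow change scores before IMP for this table and say how the three Day -1 cards give one value. Align Listing 16.2.6.3.3.
- **SAP 10.9.3 and Table 14.3.7:** use the last pre-inoculation value as baseline for the by-study-day table. Add a table by day from first IMP, with the last pre-IMP value as baseline, for the drug comparison.
- **Reconcile** Protocol section 8, Protocol 10.7.1, SAP 10.1.1, SAP 10.9.3 and the shared safety shell, stating which baseline serves which table.

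Cost: SAP wording, one more descriptive vital-signs table, and one symptom table deleted or redefined. No new data are needed. The changes should be settled before unblinding.

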10.9.4. Spirometry

Summary statistics for absolute values and change from baseline by time point will be tabulated, by group, for spirometry parameters (FEV₁(absolute), FEV₁(% predicted), Forced vital capacity (FVC) (absolute), FVC (% predicted), FEV₁/FVC ratio (absolute), FEV₁/FVC ratio (% predicted)) and will also be included within participant listings.

The spirometry baseline is the assessment performed at screening.

10.9.5. Physical Examination

Physical examination findings (both for the complete examination and also any directed examination assessments) will be included within participant listings.

10.9.6. 12-Lead Electrocardiograms

Summary statistics for absolute values and change from baseline by time point will be tabulated, by treatment group for the following ECG parameters: (Heart Rate (bpm), PR interval (sec), QRS duration (sec), QT interval (sec), QTc interval (sec), QTcB interval (sec), QTcF interval (sec) and RR interval (sec)). For all ECG parameters, the baseline assessment is defined as the assessment performed prior to IMP dosing. All data will be included within participant listings.

11. CHANGES TO THE PROTOCOL SPECIFIED ANALYSIS DETAILED IN THE STATISTICAL ANALYSIS PLAN

1. Clarity has been added to the definitions for the ITT-A and ITT-B populations to ensure they are mutually exclusive and are accounting for subjects who have a positive detection either side of IMP administration.
2. The protocol incorrectly used median AUC as the main estimator of the primary endpoint. This has been corrected within the SAP to use the mean AUC.
3. Inferential analysis was not required for any time to event secondary endpoints within the protocol. However, this have been deemed as necessary to support the study outcome and log rank tests have been added to the appropriate endpoints.
4. The endpoint 'Time (days) to peak viral culture in nasal samples, starting from initial administration of IMP' had been missed in the list of endpoints within the protocol, though referred to in later sections. This endpoint has been added to the SAP.
5. Symptom resolution was included within the wording of the secondary clinical-symptom related endpoints and referred to as 'returning to baseline score'. This was deemed not to fit the requirements of the endpoint and has instead been amended to be 24-hours symptom free.
6. The endpoint 'Time to symptom resolution ... starting at initial administration of IMP to time of returning to baseline score' has been expanded to include the caveat that the symptom-free period must occur after the peak symptom score.

13. TABLES, FIGURES AND LISTINGS

13.1. Specific Presentation Details

Tables, listings, and figures will be provided in a WORD document [and programmed off CDISC compliant SDTM SAS data sets.]. All summary tables and figures will have source data footnotes that refer to the relevant listings. Dates will appear as ddmmmyyyy; times as hh:mm. All listings will be ordered by treatment group, participant number, and scheduled visit. For the presentation of summary data, values will be aligned based on the unit column, and not left/right justified. For example:

Parameter	n	xx	xx
	Mean (SD)	xx.x (xx.xx)	xx.x (xx.xx)
	GM (GSD)	xx.x (xx.xx)	xx.x (xx.xx)
	%CV	xx.x	xx.x
	SE	xx.xx	xx.xx
	Median	xx.x	xx.x
	Q1, Q3	xx.x, xx.x	xx.x, xx.x
	Min, Max	xx, xx	xx, xx

All tables, listings and figures will have the SAS program name, output filename and date of production in the footnote.

All tables, listings and figures will include the following study header and footer:

CONFIDENTIAL

hVIVO Services Ltd
REV002 [VIR-CST-001]

Page x of y

Table x.x
Title
Participant population

Source Data: Listing 16.2.x {Source data footnote only appears for tables, where x references relevant listing number}

Program: xxxxxxxxx

Output: xxxxxxx

Date: xxxxxxxxx

